14.3. Data description and statistical analysis

Subject disposition

Data from subjects of all defined populations, from subjects who completed the study, and from subjects who withdrew from the study will be summarized by product group using descriptive statistics.

Data from subjects who withdrew from the study will also be summarized by reason for withdrawal using descriptive statistics.

Demographic and Baseline Characteristics

Subjects demographic and baseline characteristics will be summarized by product group using descriptive statistics. For continuous variables, descriptive statistics (n, mean, standard deviation, standard error, median, minimum, and maximum) will be provided. For categorical variables, subject counts and percentages will be provided. Categories for missing data will be presented if necessary.

Efficacy analyses

Analyses will use 2-sided tests at the 5% significance level, except the normality tested at the threshold of 1% (Shapiro-Wilk test).

For all parameters, descriptive statistical tables along with graphics will be performed.

For quantitative parameters (such as clinical counting of cutaneous lesions, sebumetry, corneometry, pHmetry), products will be compared by a covariance analysis with Product and Time as fixed factors, Subject as random factor and value at baseline as covariate (mixed models for repeated longitudinal using SAS® Mixed procedure). The interaction Time x Product will be tested. **Contrasts between products will be evaluated at each time. For the total number of cutaneous lesions, W12 will be considered as the primary contrast.**

Ordinal parameters such as the GEA will be analysed using generalized linear random model for multinomial data (a model for binary data can also be used according to the results of the descriptive analysis), with Subject as random factor, Time and Product as fixed factors and the value at baseline as covariate (SAS® Glimmix Procedure).

All comparisons will be carried out using contrasts. Tests will be followed by a Benjamini-Hochberg adjustment for multiple comparisons.

Data collected [from the efficacy and cosmetic acceptability questionnaires](#) at W12 will be described and compared between products by a chi-square test.

Safety analyses

Physical and functional signs will be described and analysed using a generalized linear random model for multinomial data (a model for binary data can also be used according to the results of the descriptive analysis), with Subject as random factor, Time and Product as fixed factors (SAS® Glimmix Procedure).

The overall tolerance will be compared between treatments using a chi-square test.

The adverse events will be described and the number of subjects with at least one AE related to the study product will be compared between products by a chi-square test.

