| Safety Assessments | Certificates of confirming the safety of the studied product will be provided by the Sponsor and will be included in the Investigator's brochure. The comparative product (Hydréane légère) is already on the market (cf Appendix 3 for informations). The fixed combination of "Adapalene 0.1%/ benzoyl peroxide 2.5% treatment" will be the marketed pharmaceutical drug Epiduo® 0.1%/2.5% gel; Galderma Laboratoires, as tube of 30g (cf Appendix 4). |
| Dose Regime/ Application instructions/ Randomisation | At W0, W4 and W8, subjects will be supplied with 1 tube of Epiduo® and 1 of the 2 cosmetic products according to the randomisation for a 4-week application period. Once-a-day, on the morning , the subjects will apply about a hazelnut of IP (amount equivalent to the amount generally used for a product of this type) to their face (avoiding eyes contour) in place of their usual product. Once-a-day, on the evening (before bedtime) , the subjects will apply the IP "Adapalene 0.1%/ benzoyl peroxide 2.5% treatment" on their face (affected area) on a cleansed and dried skin. The product must be applied in thin layer evenly with fingertips, avoiding eyes, lips and nostrils. The subjects will have to wash carefully their hands after each application. All IP applications will be made at home from W0 until the day before the last visit (W12) (i.e. 12-week application period). |

| | |
|-----------------------|---|
| Study duration | 12 weeks with 4 visits to the study site (W0, W4 ± 3 days, W8 ± 3 days and W12 ± 3 days) per subject. |
|-----------------------|---|

An interval of at least one month must be respected before the subject will be allowed to participate in another study.

| | |
|------------------------|-------------------------------------|
| Data Management | Double data entry will be employed. |
|------------------------|-------------------------------------|

| | |
|----------------------------|---|
| Statistical methods | Comparisons of fla 688977 33 versus Hydréane légère |
|----------------------------|---|

Statistical analysis

All data will be described by product.

1. For quantitative parameters, comparison between products using a covariance analysis with Product and Time as fixed factors, Subject as random factor and the value at baseline as covariate.

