2. For ordinal parameters, comparison between products using a generalized linear random model for multinomial data with Subject as random factor, Time and Product as fixed factors and the value at baseline as covariate.

Responsibilities

| | |
|--|---|
| Protocol writing | Intertek |
| Supply of labeled study products | 
• Dermo-cosmetic & Hydréane légère: Sponsor• Epiduo®: Investigator funded by the Sponsor |
| Products liability | Sponsor |
| Safety Assessment of the studied product | Sponsor |
| Randomization | SYLIA-STAT LANCRENON |
| Conduct of clinical phase | Each study centre |
| Monitoring | Sponsor |
| Quality assurance | Sponsor |
| Data management | SYLIA-STAT LANCRENON |
| Statistical analysis | SYLIA-STAT LANCRENON |
| Report writing without microbiota analysis | SYLIA-STAT LANCRENON |
| Microbiota analysis (if applicable) | INRA Transfert & Mercurialis for the interpretation of the results |

| | |
|------------------------|--|
| Study timelines | The planned study schedule will be as follows: |
|------------------------|--|

| | |
|--------------------------|-----------------|
| First inclusion | JAN-2019 |
| Last subject, last visit | DEC-2019 |
| Final report | DEC-2020 |

FLOW CHART

| STUDY PROCEDURES | VISIT 1 W0 Baseline | VISIT 2 ⁽¹⁾ W4 | VISIT 3 ⁽¹⁾ W8 | VISIT 4 ⁽¹⁾ W12 Final |
|---|---------------------------|------------------------------|------------------------------|--|
| Informed consent | X | | | |
| Demographics | X | | | |
| Medical history ⁽²⁾ | X | | | |
| Previous ⁽³⁾ and concomitant medication | X | | | |
| Checking of inclusion / exclusion criteria | X | | | |
| Urinary pregnancy test for females of child-bearing potential | X | | | |
| Counting of the retentional (open & closed comedones) and inflammatory lesions (papulae, pustulae & nodules (if applicable)) on the face by the Dermatologist | X | X | X | X |
| Determination of the acne stage according to the GEA scale by the Dermatologist | X | X | X | X |
| Clinical assessments by the Dermatologist (skin quality efficacy and local tolerance) | X | X | X | X |
| Microbiota sampling by a technician and/or a nurse | X | | | X |
| Instrumental measurements by a technician and/or a nurse | X | X | X | X |
| Confocal microscopy (n≈30; CHU Nantes study centre only) | X | | | X |
| Dispense IP, daily log and instructions | X | X | X | |
| Daily application of IP at home | | | X ⁽⁴⁾ | |
| Completion of daily log | | | X ⁽⁵⁾ | |

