9.4. Subject identification

The subjects will be identified by their screening number (SCXXX) and their randomisation number (RDXXXX) at W0 in order to maintain their data confidentiality.

The format of the screening number consists in letters SC followed by 3 digits; the 3 digits start from 001 and are given to the subjects in a chronological order during the screening in each study centre.

The format of the randomisation number consists in letters RD followed by 4 digits (the 1st digit corresponds to the number of the study centre); this number will be assigned to the subjects in the order of inclusion at W0 in each study centre as follow:

Intertek: from n° RD1001 to RD1100

CHU Nantes: from RD2001 to RD2100

The subject numbers will be documented in the CRF.

Subjects will be identified to the Sponsor only by their subject numbers, date of birth and gender. All subjects included in the study will be listed in the study status table.

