9.5.1. Description of randomisation/blinding measures

Prior to the start of the study, a randomisation list will be drawn up by SYLIA-STAT LANCRENON to be transmitted to the clinical packaging organisations for labelling.

The labels of the product materials identify only the randomisation number.

Subjects who fulfils all criteria will be randomized at each study centre in 1:1 way to receive:

- The dermo-cosmetic product (fla 688977 33)
- The standard moisturizer

The first IP will be dispensed to the subjects in the chronological order of their inclusion in the study at the visit 1, and no number should be omitted or skipped. This number will be documented in the CRF.

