11.6. Study assessments

For 1 subject, clinical assessments should be performed by the same investigator for the whole study except in case of absolute necessity.

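### Randomisation is 1:1 within each of two centres, but no product comparison includes Centre; precision is lost if the centres still differ at W12 after baseline adjustment

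*Combined protocol and SAP*

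**What the plan says.** **Allocation.** Section 9.5.1 states: "Subjects who fulfils all criteria will be randomized at each study centre in 1:1 way to receive" one of the two cosmetic products. Under section 9.4 the randomisation number is "assigned to the subjects in the order of inclusion at W0 in each study centre", running from RD1001 to RD1100 at Intertek and from RD2001 to RD2100 at CHU Nantes. No block size is given.

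**Analysis.**
- Quantitative endpoints, including the primary W12 contrast on total lesions: a "covariance analysis with Product and Time as fixed factors, Subject as random factor and value at baseline as covariate" (section 14.3). The synopsis agrees: "comparison between products using a covariance analysis with Product and Time as fixed factors".
- Ordinal efficacy endpoints such as the GEA: "generalized linear random model for multinomial data with Subject as random factor, Time and Product as fixed factors", plus baseline (synopsis, repeated in section 14.3).
- Physical and functional tolerance signs: a multinomial model "with Subject as random factor, Time and Product as fixed factors (SAS® Glimmix Procedure"), with no baseline covariate.
- Overall tolerance: "The overall tolerance will be compared between treatments using a chi-square test". The W12 questionnaires and product-related adverse events are also compared by plain chi-square tests.

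Centre is not named anywhere as a factor, stratum, interaction or subgroup. Section 14 says that a separate SAP will be approved before database lock, but does not say that it will add Centre.

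**The concern.** When the allocation is organised by centre, the analysis should normally reflect that. If it does not, any centre difference that baseline leaves unexplained stays in the residual variance. The random Subject effect does not recover it, because Product is tested against the between-subject variance, where the centre difference sits.

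Some difference is plausible, although the documents give no size. Intertek recruits from a database, social media and its website, while Nantes recruits through consultations and mailings (section 9). Raters differ between centres. Instrumental measurements are made by a technician at one centre and a nurse at the other (section 11.6.2.2); that last contrast does not touch the primary count.

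At stake is power in a trial planned at only 80%. The linear treatment contrast is not biased and false positives do not increase.

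**Working it through.** **Inputs.** From section 14.1: difference 1.15 lesions, SD 5.0, R² = 0.70, two-sided 5%, 80% power, 90 evaluable per arm, 10% drop-out. From section 9.4: two centres with 100 numbers each, so equal centres are used below. Assumed: d, the baseline-adjusted centre difference at W12, from 0 to 3 lesions.

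**1. The plan's own figure.** Residual variance = 25 × (1 − 0.70) = 7.5. Per arm, n = 2 × 7.5 × (1.960 + 0.842)² / 1.15² = 89.0, rounded up to 90. Then 180 / 0.9 = 200. Both stated figures reproduce. At 90 per arm, SE = √(2 × 7.5 / 90) = 0.408 and power = Φ(1.15/0.408 − 1.960) = 80.4%.

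**2. Reading A: 7.5 is the within-centre variance; allocation balanced within centre.** Leaving Centre out adds d²/4 to the residual variance. The true SE stays at 0.408, but the reported SE is multiplied by k = √((7.5 + d²/4)/7.5). Type I error is 2Φ(−1.960k) and power is Φ(1.15/0.408 − 1.960k).

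| d | k | Type I error, no Centre | Power, no Centre | Power, with Centre |
|---|---|---|---|---|
| 0 | 1.000 | 5.0% | 80.4% | 80.4% |
| 0.5 | 1.004 | 4.9% | 80.2% | 80.4% |
| 1 | 1.017 | 4.6% | 79.5% | 80.4% |
| 2 | 1.065 | 3.7% | 76.7% | 80.4% |
| 3 | 1.140 | 2.5% | 72.0% | 80.4% |

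**3. Simulation of the planned repeated-measures model.** Visits W4, W8 and W12, W12 contrast, 20,000 trials per cell, assumed within-subject residual correlation 0.6 and constant d. Pairs are without / with Centre.

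| d | Balanced: type I error | Balanced: power | Unrestricted: type I error (without only) | Unrestricted: power |
|---|---|---|---|---|
| 0 | 5.0 / 5.0% | 80.0 / 80.0% | 4.8% | 79.5 / 79.4% |
| 0.5 | 4.7 / 4.8% | 79.7 / 79.9% | 4.9% | 78.7 / 78.7% |
| 1 | 4.6 / 4.9% | 79.3 / 80.4% | 4.9% | 78.3 / 79.1% |
| 2 | 3.7 / 5.0% | 76.4 / 80.2% | 4.9% | 74.3 / 79.2% |
| 3 | 2.4 / 4.6% | 71.0 / 80.1% | 5.1% | 67.9 / 79.2% |

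The balanced columns agree with step 2. With unrestricted allocation within centre, type I error stays near 5% and only power is lost.

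**4. Reading B: 7.5 already contains the centre difference.** The within-centre variance is then 7.5 − d²/4. With balanced allocation, power without / with Centre is 80.5 / 80.8% (d = 0.5), 80.8 / 81.7% (d = 1), 82.1 / 85.7% (d = 2) and 84.7 / 92.0% (d = 3).

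**5. Chi-square tests.** For a binary item, with an assumed 50 per arm per centre and odds ratio 2.25, chi-square / Cochran-Mantel-Haenszel (CMH) power is 80.2 / 80.2% with both centre rates at 50%, 77.8 / 78.1% at 40% and 60%, and 68.4 / 73.3% at 30% and 70%. At rates more typical of adverse events it is 41.7 / 41.8% (5% and 10%), 47.9 / 48.9% (5% and 15%) and 64.6 / 67.8% (10% and 30%). For a five-level item with assumed response distributions, chi-square against general-association CMH gives 71.0 / 70.9% when the centres agree and 60.2 / 69.7% when they differ.

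**The case against.** The loss depends on a quantity that nobody knows. For lesion counts the baseline covariate removes part of any stable difference, and section 11.6 asks that for each subject "clinical assessments should be performed by the same investigator for the whole study except in case of absolute necessity". Up to d = 1 the loss is about one power point (0.9 by formula, 1.1 in the balanced simulation). The larger losses need d of 2 to 3 lesions, which is 1.7 to 2.6 times the 1.15 treatment effect (2/1.15 and 3/1.15). Section 14.1 does not say whether the SD of 5.0 is within-centre; under Reading B the plan reaches 80% as it stands. The SAP could still add Centre. No gain was quantified for the ordinal Glimmix models or the instrumental measures. Nor is CMH a single test: the questionnaires have five levels and overall tolerance four, and a row-mean-score version would change the hypothesis.

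Most of this is right about size, and it keeps the point in the efficiency class. It does not remove the point. Baseline cannot absorb a difference that remains at W12, the tolerance-sign model has no baseline term, and the chi-square tests adjust for nothing. Under Reading B, Centre still raises power. The protocol already states its models, and a SAP still to come does not put Centre into them. The CMH objection is met by naming the general-association form, which keeps the hypothesis of the plain chi-square test.

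**Conclusion.** The concern holds. The trial randomises within two centres and no product comparison uses Centre. The defect is one of efficiency: the linear contrast is unbiased, and type I error is at or below about 5%. For the primary endpoint under Reading A, the balanced-case loss is about 1 power point at d = 1, 4 at d = 2 and 8 to 9 at d = 3, and nothing at d = 0. Under Reading B nothing is lost against plan, but a gain of 0.9 points at d = 1 and 3.6 at d = 2 is forgone.

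These sizes rest on an assumed d, equal centres, 90 evaluable per arm and, for the conservative type I error, balance within centre. No block size is stated, and per-protocol exclusions could weaken that balance. No size is claimed for the ordinal models or the instrumental measures. The change should be made, chiefly because it costs almost nothing.

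**What to change.** Before database lock, and ideally in section 14.3 as well as the SAP:

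- Add Centre as a fixed factor to the mixed models for lesion counts, sebumetry, corneometry and pH, and to the Glimmix models for GEA and the tolerance signs.
- Replace the plain chi-square tests (questionnaires, overall tolerance, related adverse events) with centre-stratified CMH tests, naming the general-association version.
- Exempt the confocal microscopy measures. They are taken at Nantes only, so Centre cannot be estimated.
- State whether the randomisation list is blocked within centre.

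The cost is SAP wording and one degree of freedom per model. In the balanced simulation at d = 0, power is 80.0% with and without Centre. Centre is already the first digit of the randomisation number, so no new data are needed and the sample size stays at 200.

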14.1. Sample size calculation

The primary objective of this study is to demonstrate the superiority of fla 688977 33 versus Hydréane légère on the total number of lesions at W12.

The following hypotheses, based on previous studies (4) were used for the estimation of the sample size calculation:

- Power $(1 - \beta) = 80\%$
- Two-sided significance level $(\alpha) = 5\%$
- Expected inter-treatment difference (on the changes W12-W0) = 1.15
- Standard deviation = 5.0
- Correlation between the baseline and the endpoint $R^2 = 0.70$

Using the sample size calculation method for covariance analysis (7), the number of evaluable subjects is estimated at 90 by treatment group (180 subjects total).

If we anticipated 10% of drop-out, the total number of subjects required is 200.

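### The primary W12 contrast is written with a random subject and a single baseline covariate and no covariance structure; read plainly, it pools variance and baseline slope over W4, W8 and W12, so its standard error or efficiency can suffer if these differ by visit

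*Combined protocol and SAP*

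**What the plan says.** Section 14.3 (Efficacy analyses) compares the products on quantitative parameters, including lesion counts, by a covariance analysis with "Product and Time as fixed factors, Subject as random factor and value at baseline as covariate", run in the SAS Mixed procedure for repeated longitudinal data. It adds that "The interaction Time x Product will be tested", that product contrasts are taken at every visit, and that for total lesions "W12 will be considered as the primary contrast". The synopsis (section 4, Statistical methods) gives the same factors. Neither place names a covariance type, visit-specific variances, a baseline-by-time term, a degrees-of-freedom method or a centre term.

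Section 14.1 sizes the trial with an analysis-of-covariance formula for one baseline and one endpoint: "Expected inter-treatment difference (on the changes W12-W0) = 1.15" and "Standard deviation = 5.0", with an R² of 0.70 between baseline and endpoint. Section 9.5.1 says that subjects "will be randomized at each study centre in 1:1 way". Section 14 announces a separate SAP before database lock, and 9.5.2 has the code broken after lock.

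**The concern.** A random subject effect with nothing else stated is a random-intercept model. It gives the three post-baseline visits the same variance and every pair of visits the same correlation. A single baseline covariate gives the three visits the same slope on baseline. Lesion counts are taken at W4, W8 and W12 under active treatment, and the documents give no ground for assuming that their spread, or their relation to baseline, stays the same throughout.

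The test that decides the trial concerns W12 alone. Under the written model its standard error comes from a variance averaged over three visits, and its baseline adjustment uses a slope averaged over three visits. The first can move the type I error away from 5% in either direction. The second can cost power even when the error rate is right.

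**Working it through.** **Inputs from the documents.** Two-sided 5% level (14.3); power 80%, difference 1.15, SD 5.0, R² 0.70, 90 evaluable per arm and 10% drop-out (14.1). The 0.70 is read as a squared correlation, the reading that returns the plan's own number.

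**Assumed.** SDs and baseline correlations at W4 and W8, which the documents do not give; 5.0 taken as the SD of the W12 count; complete data at all three visits.

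**Step 1: the plan's figure.** n per arm = (1 − R²) × 2 × [SD × (1.960 + 0.842)/1.15]² = 0.30 × 296.7 = 89.02, hence 90. Power at 90 is 80.4% (normal) or 80.0% (t). 180/0.90 = 200. The figure reproduces, for an analysis of covariance at W12 alone, whose standard error is 5 × √0.30 × √(2/90) = 0.408.

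**Step 2: the written model on complete data.** Let s be the SD and r the baseline correlation at a visit.
- Residual variance about the visit's own slope: v = s²(1 − r²).
- Cost of the common slope: e = (r·s − mean of r·s over the three visits)². The baseline SD cancels.
- Model SE = √[mean over visits of (v + e) × 2/90].
- True SE at W12 = √[(v + e at W12) × 2/90].
- Type I error = 2 × P(Z > 1.96 × model SE/true SE).
- Power is taken at the difference for which the W12 analysis of covariance has 80%. With r rounded to 0.84 (√0.70 = 0.837), its SE is √(7.36 × 2/90) = 0.404, so the difference is 2.80 × 0.404 = 1.13.

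**Step 3: one pattern in full.** SDs 7, 6, 5 and r = 0.84 throughout. v = 14.43, 10.60, 7.36. r·s = 5.88, 5.04, 4.20, so e = 0.71, 0, 0.71. Then v + e = 15.13, 10.60, 8.07, with mean 11.27. Model SE = 0.500 and true SE = 0.423, so the model SE is 18% too large. Type I error is 2.1% and power is 64%.

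**Step 4: the range.**

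| SD at W4/W8/W12 | r at W4/W8/W12 | Model SE | True SE | Type I | Power |
|---|---|---|---|---|---|
| 5/5/5 | 0.84/0.84/0.84 | 0.404 | 0.404 | 5.0% | 80% |
| 7/6/5 | 0.84/0.84/0.84 | 0.500 | 0.423 | 2.1% | 64% |
| 8/6.5/5 | 0.92/0.88/0.84 | 0.485 | 0.467 | 4.2% | 65% |
| 7/6/5 | 0.92/0.88/0.84 | 0.435 | 0.437 | 5.1% | 74% |
| 6/5.5/5 | 0.90/0.87/0.84 | 0.406 | 0.414 | 5.4% | 79% |
| 5.5/5.25/5 | 0.88/0.86/0.84 | 0.400 | 0.407 | 5.4% | 80% |
| 6/5.5/5 | 0.92/0.88/0.84 | 0.390 | 0.416 | 6.6% | 81% |
| 5/5/5 | 0.92/0.88/0.84 | 0.354 | 0.406 | 8.7% | 86% |
| 4/4.5/5 | 0.90/0.87/0.84 | 0.339 | 0.407 | 10.3% | 88% |

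In the last three rows, power at or above 80% goes with a type I error above 5% and is no gain.

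**Step 5: check.** The calculation was repeated with R² exactly 0.70 at W12 and the planned 1.15. SDs 7/6/5 with constant R² give type I error 2.1% and power 64.7%. The milder 6/5.5/5 with constant R² gives 3.2% and 73.7%. SDs 7/6/5 with R² 0.85/0.78/0.70 give 5.4% and 75.2%. Equal SDs with R² 0.85/0.78/0.70 give type I error 9.1%. Simulation of 4000 trials per pattern agreed to within about one percentage point. A W12-specific analysis held about 80% power and a simulated type I error of about 5–6% in every pattern.

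**The case against.** The strongest reply is that the defect is read out of silence. The reference to mixed models for repeated longitudinal data leaves room for a REPEATED statement with a richer covariance, and the SAP due before lock is the usual place to name it. That stands as far as it goes: the pooled variance and common slope are the plain reading, not words in the text. But neither 14.3 nor the synopsis commits to anything richer, and the single baseline covariate is explicit in both.

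A second reply also stands in part. If the spread falls and the link to baseline weakens together, the two effects pull the model SE in opposite directions. The table shows patterns where little is lost. The largest type I errors need either a weakening correlation with no fall in SD, or an SD that rises during treatment.

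Three stronger readings are tempting, and the documents do not support them:
- **That testing Time x Product allows it to be dropped, leaving a three-visit average.** Section 14.3 requires product contrasts at each visit with W12 primary. That needs the interaction in the model, and no rule for removing it appears.
- **That any departure from constant variance and slope corrupts the error rate.** SDs 7/6/5 with correlations 0.92/0.88/0.84 give 5.1%. There the loss is in power, about 74%.
- **That the sample size is wrong because it assumes a W12 analysis of covariance.** The 90 per arm reproduces, and the written model gives the same SE of 0.408 when variance and slope are constant.

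**Conclusion.** The point holds as a weakness in how the primary model is specified, with a clearly better model available. Under the plain reading of 14.3, type I error for the W12 contrast runs from about 2% to 10% over the main patterns tabulated, and power falls to about 64–75% in the larger falling-SD cases. With constant variance and slope there is no harm. With mild, offsetting changes the figures are about 5.4% and 79–80%.

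All of this rests on assumed W4 and W8 SDs and correlations, complete data, a W12 SD of 5.0 and 90 per arm. A reader might infer that the primary test in this trial is in fact inflated or underpowered. The documents cannot show that, because they give one SD and one R² only. What they do show is that the level set by "Analyses will use 2-sided tests at the 5% significance level" would depend, for the deciding test, on visit patterns that the plan neither states nor supports.

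**What to change.** In 14.3, with the synopsis aligned, and in the SAP before unblinding, state the primary model as a repeated-measures model of the W4, W8 and W12 counts with:
- fixed effects Product, Time, Product x Time, Baseline, Baseline x Time and Centre, the last because randomisation is done within centre;
- unstructured within-subject covariance (REPEATED, TYPE=UN) and no random intercept;
- Kenward-Roger degrees of freedom;
- the W12 Product contrast as the primary test;
- a named fallback covariance if the model does not converge, preferably one that keeps visit-specific variances.

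On complete data, and before Centre is added, the W12 contrast then equals the analysis of covariance used for sizing in 14.1: SE 0.408 and power 80.4% at 90 per arm. The effect of Centre was not computed.

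The cost is a few more parameters: six covariance parameters instead of two, two further baseline slopes and one centre term, with about 180 evaluable subjects. No visit, subject or measurement is added.

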7.2. Secondary objectives

The secondary objective of the present study are:

- To evaluate the effects on the skin quality of the dermo-cosmetic product associated with the fixed combination Adapalene 0.1% / benzoyl peroxide 2.5% treatment versus this treatment associated with a standard moisturizer.
- To demonstrate that the dermo-cosmetic product can improve the local tolerance of the fixed combination Adapalene 0.1% / benzoyl peroxide 2.5% treatment compared to a standard moisturizer.

- To evaluate the cosmetic acceptability of the dermo-cosmetic product versus a standard moisturizer.
- According to the results of the primary variable, to evaluate the impact on the microbiota of the dermo-cosmetic product associated with the fixed combination Adapalene 0.1% / benzoyl peroxide 2.5% treatment versus this treatment associated with a standard moisturizer.
- To collect safety data.

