11.6.2.3. Local tolerance

- Clinical assessments

At W0 (before any application), W4 (after a 4-week application period), W8 (after an 8-week application period) and W12 (after a 12-week application period), a clinical assessment of the face skin condition will be performed by the Dermatologist:

- Physical signs: erythema, dryness and scaling
- Functional signs*: tightness, prickling, itching, burning sensation and others

The following scale will be used:

Rating 0: none ("absence")

Rating 1: slight ("léger")

Rating 2: moderate ("modéré")

Rating 3: severe ("sévère")

* During the study, the subjects will have to record any skin discomfort, intensity (slight, moderate or severe) and duration in their daily log. Functional signs will be assessed by the Dermatologist from a review of the daily log and interrogatory of the subject.

- Overall tolerance

In addition, at W12 (after a 12-week application period), the Dermatologist and the subject will state about the overall tolerance of the IP (cosmetic product & drug) based on rating scale:

- Excellent tolerance
- Good tolerance
- Medium tolerance
- Poor tolerance

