14. SAMPLE SIZE / STATISTICAL ANALYSIS

A statistical analysis plan (SAP) will be prepared by the SYLIA-STAT LANCRENON and validated by the Sponsor prior to the database lock. Statistical analyses will be performed with SAS® version 9.4 or higher (SAS institute, North Carolina, USA).

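### The local-tolerance model omits the baseline covariate that the synopsis sets for ordinal parameters and that Section 14.3 applies to GEA

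*Combined protocol and SAP*

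**What the plan says.** The Statistical methods entry of the synopsis (Section 4) has one rule for product comparisons on ordinal parameters: a multinomial random-effects model with "Subject as random factor, Time and Product as fixed factors and the value at baseline as covariate". It draws no line between efficacy and safety.

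The Efficacy analyses part of Section 14.3 repeats the rule for GEA and similar scores: "Time and Product as fixed factors and the value at baseline as covariate (SAS® Glimmix Procedure".

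The Safety analyses part of Section 14.3 takes up the physical and functional signs in nearly the same sentence but stops earlier: "with Subject as random factor, Time and Product as fixed factors (SAS® Glimmix Procedure". No baseline term follows and no reason is given. It does not say whether W0 is left out or is a level of Time, and it names no Product x Time term. Section 14.3 states that interaction for the quantitative parameters only.

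The signs do have a baseline value. Section 11.6.2.3 has the dermatologist grade them from 0 (none) to 3 (severe) "At W0 (before any application), W4 (after a 4-week application period), W8 (after an 8-week application period) and W12". Section 7.2 makes them a comparative objective: "To demonstrate that the dermo-cosmetic product can improve the local tolerance of the fixed combination".

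**The concern.** The same ordinal scores fall under two different models, depending on whether one follows the synopsis or the body. The version in the body discards information that is already collected. If a subject's signs tend to persist from visit to visit, the W0 score explains part of the between-subject variation. Leaving it out then widens the interval for the product difference and lowers the chance of showing a real tolerance benefit.

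A second risk comes from the silence on W0. If W0 were entered as a level of Time with main effects only, the Product effect would be averaged over a visit at which no product had yet been applied, and so would be diluted.

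Neither the primary lesion analysis nor the validity of the tolerance test is at stake. What is at stake is the precision of a secondary comparison that the protocol sets out to demonstrate, and an analyst's choice that should be closed before unblinding.

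**Working it through.** **The plan's own figure.** There is none for tolerance. Section 14.1 powers only the lesion count: 2 x (5.0 x (1.960 + 0.842)/1.15)^2 = 296.7; times (1 - 0.70) = 89.02, rounded up to 90 per group; 180/0.9 = 200. That reproduces and is unaffected by this point.

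**Assumed inputs.** The documents give no correlation, distribution or target power for the signs. Assumed here: power of 80% with the W0 covariate, two-sided 5%; correlation r among W4, W8 and W12; correlation r0 between W0 and later visits; unit variance at each visit; a linear approximation.

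**Product effect pooled over W4, W8 and W12.**

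- Variance without W0 is proportional to (1 + 2r)/3.
- Variance with W0 as covariate is proportional to (1 + 2r)/3 - r0^2.
- Power without W0 = Phi(2.802 x sqrt(variance with / variance without) - 1.960).

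Example, r = r0 = 0.3: 0.5333 without and 0.4433 with; the ratio 0.5333/0.4433 = 1.20 means 20% more subjects; 2.802 x sqrt(0.4433/0.5333) - 1.960 = 0.594, so power is 72.4%.

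**Single-visit contrast.** The variance ratio is 1/(1 - r0^2). Example, r0 = 0.3: 1/0.91 = 1.10; 2.802 x sqrt(0.91) - 1.960 = 0.713, so power is 76.2%.

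| r | r0 | Pooled: power without W0 (extra subjects) | By visit: power without W0 (extra subjects) |
|---|---|---|---|
| 0.1 | 0.1 | 79.0% (3%) | 79.6% (1%) |
| 0.2 | 0.2 | 76.4% (9%) | 78.4% (4%) |
| 0.3 | 0.3 | 72.4% (20%) | 76.2% (10%) |
| 0.5 | 0.5 | 60.1% (60%) | 67.9% (33%) |
| 0.3 | 0.15 | 78.3% (4%) | 79.1% (2%) |
| 0.5 | 0.25 | 76.0% (10%) | 77.4% (7%) |

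**W0 as a Time level, main effects only.** The effect shrinks to 3/4 and the variance becomes (1 + 3r)/4. At r = r0 = 0.3: 2.802 x 0.75 x sqrt(0.4433/0.475) - 1.960 = 0.070, power 53%. At 0.5 the same steps give 40%.

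**Ordinal simulation.** Cumulative-logit random-intercept model (11-point quadrature, Wald test, Python rather than SAS), 95 per arm assumed, 1,400 trials per case (Monte Carlo standard error about 1 point), pooled effect set for about 80% power with the covariate. Categories 0-3 occur at 50/30/15/5%.

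| Score correlation | W0 covariate | W0 left out | W0 as response, common baseline | W0 as Time level, main effects only |
|---|---|---|---|---|
| 0.08 | 81.5% | 80.8% | 81.6% | 64.9% |
| 0.20 | 83.9% | 80.6% | 83.9% | 64.0% |
| 0.30 | 80.3% | 73.8% | 80.3% | 53.9% |
| 0.52 | 81.1% | 59.9% | 80.9% | 40.1% |

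Two further cases: with 75% of scores at 0 (correlation 0.24), 79.1% with the covariate and 74.2% without. With signs rarer at W0 than later (r0 = 0.26, r = 0.31), 82.0% and 76.2%. Type I error under the null was 4.6% with the covariate, 3.9% without and 4.4% with a common baseline. None of 35,000 fits failed.

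**The case against.** The strongest reply concerns size. The larger losses belong to a Product effect pooled over three visits. Section 14.3 asks for contrasts at each time for the quantitative parameters and then says "All comparisons will be carried out using contrasts", so by-visit contrasts for the signs are plausible. On that reading the loss at r of 0.2 to 0.3 is about 2 to 4 points. This stands, and the table shows both readings. The pooled figure fits the literal safety model, which names only main effects of Time and Product.

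The W0 link may also be weak. W0 scores precede any application, Section 9.3 excludes other confounding facial dermatoses and restricts recent topical drugs and some cosmetics, and later scores are rated under the drug. Functional signs are rated partly from a daily log that is first dispensed at W0 (Section 11.5). This is fair inference, though the documents hold no data to settle it. If most W0 scores are 0, little is lost. The simulated case with rarer signs at W0 does not test a weak link, since its r0 is nearly as high as r; only the last two rows of the first table do.

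The main-effects row needs a reading that the protocol does not state. It is conditional, and it shows why the role of W0 must be written down.

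Finally, the synopsis is a summary, and a separate SAP is still to be "validated by the Sponsor prior to the database lock". A specific safety paragraph could be read as governing. But the synopsis rule is not limited to efficacy, the body gives no reason to depart from it, and the SAP author has two conflicting instructions. That the SAP can settle the point is a reason to settle it there.

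**Conclusion.** The concern holds. Synopsis and body specify different models for the same ordinal scores, and the body's version is the less precise one. Under randomisation there is no bias and no type I error inflation, and the primary analysis and sample size are untouched.

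The loss cannot be fixed from the documents. For a pooled Product effect it is negligible at a visit correlation near 0.1, moderate at 0.2 to 0.3 (80% falling to 76% and 72%) and large only near 0.5 (60%). By-visit contrasts or a weak W0 link shrink it, to between 76% and 79% in the weak-link cases shown. All of this rests on assumed correlations, an assumed 80% anchor and, in the simulation, assumed category frequencies. The change is worth making because it costs almost nothing and serves an objective worded as a demonstration.

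**What to change.** Bring the safety paragraph of Section 14.3 into line with the synopsis: model W4, W8 and W12 as responses, with the W0 score of the same sign as covariate. An equivalent choice is to keep W0 as a response with a common baseline in both arms and a Product x Time term. If the omission is deliberate, give the reason and correct the synopsis. Either way, state in the SAP how W0 enters.

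Two minor clarifications, not errors, apply to GEA and the signs alike. The option that "a model for binary data can also be used according to the results of the descriptive analysis" has no stated rule; any collapse to binary, with its cut-point, can be set on pooled data at the blind review planned in Section 13.3, before lock and the general code break (Section 9.5.2). The SAP should also say whether the ordinal contrasts are by visit and whether the contrast statement covers the safety models.

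The cost is one line of SAP text for the main change, with no new data, visits or subjects. The added term could cause convergence problems for rare signs; none occurred with up to 75% of scores at 0, but rarer signs were not tested. The covariate may also help less for functional signs.
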